7.3 Investigational Plan

Subjects' preoperative MRI and their history will be reviewed at the weekly CUIMC Pediatric Neuro-Oncology Tumor Board to determine disease status, and to confirm eligibility criteria and to schedule the admission date. A recent (no longer than 7 days prior to the time of the procedure) MRI with and without Gadolinium contrast that includes T1, T2, and FLAIR is required, otherwise the MRI will have to be repeated.

On the day of admission, the subject will present to the Pediatric Oncology Outpatient clinic and will be brought to the Radiation Oncology Suite (for the Navigator-Guided Focused Ultrasound (NgFUS)) (Children Hospital of New York (CHONY) Floor 3) and subsequently to the Pediatric Oncology outpatient clinic (HIP-7). Institutional policies regarding COVID for transportation will be followed.

Columbia University Irving Medical Center
Protocol Version 4.0 Date: 12.10.2021

In the radiation oncology suite, under the supervision of the Pediatric Oncology and Radiation Oncology teams, the subject will undergo:

- Focused Ultrasound and injection of DEFINITY® Microbubbles using the NgFUS system with the following ultrasonic parameters and microbubble dose:

Table I: NgFUS treatment parameters

| | |
|------------------------------------|----------------------------------------|
| FUS frequency | 0.25 MHz |
| Acoustic pressure | 200 kPa _{pk-neg} |
| Pulse length | 2,500 cycles or 10 ms |
| Pulse repetition frequency | 2 Hz |
| Total sonication time per location | 2 min |
| Definity microbubble dose | 10 µl/kg |
| Number of Tumor sites | Level A: 1 Level B: 2 Level C: 3 |

[figure not shown]
FUS will be aimed for non-enhancing peritumoral areas. Even if there is some contrast enhancement before FUS, this should be clearly increased following FUS. The focal area is quite big (6mm x 6mm x 49mm), so there should be clear opening in the neighboring non-enhancing tissue.

The total estimated time for the FUS procedure is 30-45 min.

Subjects will be sonicated, according to the pre-treatment MRI. Following the NgFUS procedure, subjects will be brought back to the Pediatric Oncology Outpatient clinic where they will receive the oral Panobinostat 15 mg/m².

During the mid-cycle at different time-points (as described in section [7.4](#) and [7.5](#) below), MRIs with gadolinium contrast will be conducted to ensure proper opening and closure of the BBB. If the subject's MRI shows any anomaly, the subject will be removed from the study and will continue on regular drug treatment as decided by the study team. The subject will follow the schema below.

7.4 Schematic Overview of Panobinostat Treatment for Week 1** Cycle 1

**Week 2 of each cycle will follow a similar schema with the exception of MRIs with contrast conducted to evaluate opening and closing of the BBB.

**Cycles 2 and 4 will follow a similar schema with the exception of an MRI to confirm closure of the BBB on Day 3.

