7.6.3 Additional MRIs to Confirm BBB Closure

The following steps will be taken if at any time any of the MRIs conducted to confirm whether the BBB is open or closed according to the definitions laid in sections [7.6.1](#) or [7.6.2](#) are unmet:

If the MRI to confirm the closure of the BBB on Day 3 does not show evidence of closure:

- subjects will no longer receive another NgFUS treatment on Day 3 to open the blood brain barrier.
- Instead, subjects will receive their scheduled Day 3 dose of Panobinostat and another MRI to confirm closure of the blood brain barrier on Day 5 prior to the scheduled FUS treatment.
- An MRI to confirm closure will be repeated every 48 hours (for a maximum of 3 times) to confirm closure in case of evidence of persistence of opening.
- If the MRI fails to show closure after 3 MRIs, Early Stopping Guidelines and Withdrawal criteria from [section 12.3](#) will be followed.
- Subjects whose BBB takes longer than anticipated to show closure will also receive an additional MRI to confirm closure in the subsequent cycle (even if not planned in the initial study schema).

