12.3 Early Stopping Guidelines

In the event 2 DLTs occur for more than 1 subject at a NOTS (number of tumor sites) level (as defined in [section 7.2](#)), study enrollment will be immediately halted. There will be at least 14 days following completion of the FUS treatment of the patient(s) on study before any subsequent patient is enrolled. After re-evaluation and consultation with the HICCC DSMC board, the trial may re-initiate enrollment with adjusted treatment parameters after a consensus is agreed upon by the Sponsor-Investigator and the HICCC DSMC, and a subsequent modification is reviewed/approved by the local PRMC/IRB. If a consensus cannot be reached, no further enrollment will be permitted on the trial and closure procedures will be initiated. In addition, the study will be discontinued at any given time if more than 20% of patients experiencing medical complications including the development of significant, irreversible deterioration during the treatment. With this rule and under the assumption of the true probability of having the medical complication is 10%, the probability of stopping the study due to the medical complication is 0.02 when the targeted total sample size is 6 and is 0.053 when the targeted total sample size is 9.

If the MRI to confirm opening of the BBB for any subject is irregular at any time during the cycles, the subject will not receive the scheduled dose treatment until a decision is made by the investigating team.

If the MRI confirm the closure of the BBB for any subject are irregular at any time, the subject will not receive any further FUS treatments and will receive another MRI to confirm closure every 48 hours for a maximum of 3 times. If the subject does not show BBB closure after 3 MRIs, the subject will come off the study. The subject will be able to receive the scheduled dose of drug, unless otherwise specified by the investigating team.

Response and progression will be evaluated in this study using the international criteria proposed by the updated Pediatric Response Assessment in Neuro-oncology (RANO) guidelines[49].

| Criterion | Complete Response | Partial Response | Stable Disease | Progressive Disease |
|----------------------------------------|---------------------|---------------------|---------------------------------|---------------------|
| T1-weighted post-Gd measurable disease | None | ≥50% decrease | <50% decrease but <25% increase | ≥25% increase |

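### A closure MRI that does not show closure has three different consequences in 7.3, 7.6.3 and 12.3, and a failed opening MRI has up to two; the sections need to be reconciled

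*Combined protocol and SAP*

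**What the plan says.** Four sections deal with what follows an unexpected MRI result.

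- **7.3** states that "MRIs with gadolinium contrast will be conducted to ensure proper opening and closure of the BBB". The next sentence reads "If the subject's MRI shows any anomaly, the subject will be removed from the study", with further drug treatment left to the study team. It does not say what counts as an anomaly.
- **7.6.3** is introduced as covering MRIs meant to show either opening or closure, but its steps concern closure only. After a Day 3 scan without closure, "subjects will no longer receive another NgFUS treatment on Day 3 to open the blood brain barrier". The subject takes the Day 3 drug dose and has "another MRI to confirm closure of the blood brain barrier on Day 5 prior to the scheduled FUS treatment". Rescans follow at 48-hour intervals, three at most, and 12.3 is invoked only if these fail to show closure. It adds: "Subjects whose BBB takes longer than anticipated to show closure will also receive an additional MRI to confirm closure in the subsequent cycle".
- **12.3** says that after an irregular closure MRI "the subject will not receive any further FUS treatments". It sets the same series of up to three rescans, allows the scheduled drug dose unless the team decides otherwise, and takes the subject off study only if closure is still not shown. After an irregular opening MRI, it withholds the scheduled dose until the investigating team decides. *Irregular* is not defined.
- **13.2** mentions the scans for opening and closing and then requires immediate withdrawal for incidental findings, with hemorrhage and structural abnormality among its examples.

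On the analysis side, 10.1 counts the method as successful if the BBB is safely opened in at least 75% of cases. It does not define a case. Section 10.2 names no analysis set.

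**The concern.** Delayed closure and failed opening are central outcomes of a study whose primary objective is to open the BBB safely and confirm that it closes. A team following 7.3, 7.6.3 or 12.3 could treat the same scan result differently: end participation, skip one session, or stop FUS while keeping the subject on study.

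The protocol itself expects these events. Section 7.6.3 plans for late closure and 12.6 plans for non-opening. Section 2.2 reports restoration in 2 to 4 days in non-human primates, whereas the closure MRI is done 24 to 48 hours after the Day 1 FUS. The human reports in 2.3 describe resolution at about 20 hours or 1 day, so how often late closure will occur is uncertain.

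At stake are the FUS exposure of such a subject, whether that subject can reach NOTS Levels B and C and add to the safety data there, and how many opening scans the subject supplies.

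**Working it through.** The plan gives no figure on this point. Its only sample-size figure, 6 subjects in 10.1, reproduces: d = 72/50 = 1.44, and a two-sided paired t-test at 0.05 has power 0.677 with 5 subjects and 0.803 with 6. It is not in dispute here.

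**Step 1. Closure MRI on Day 3 does not show closure**

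| Section | Later FUS | Participation |
|---|---|---|
| 7.3, if *anomaly* includes non-closure | None | Ends at this finding |
| 7.6.3 | Day 3 omitted; Day 5 still scheduled after a rescan; a later cycle foreseen | Continues; 12.3 applied after three scans without closure |
| 12.3, as worded | None | Continues; ends after three scans without closure |

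The rows for 7.6.3 and 12.3 agree on rescanning, drug and the off-study trigger. They differ on whether FUS can be given again. The row for 7.3 differs from both on participation.

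**Step 2. Opening MRI does not show opening**

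Section 7.3, on the same reading, removes the subject; 12.3 holds the dose until a decision. Section 7.6.3 lists no step, and the bar on further FUS in 12.3 is attached to closure only.

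**Step 3. Exposure after non-closure at Cycle 1 Day 3**

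Inputs from 7.2 and 7.5: 6 cycles; 2 weeks of 3 treatment days per cycle; one opening MRI per cycle, on Week 1 Day 1; sites per cycle 1, 1, 2, 2, 3, 3.

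- Planned FUS days: 6 × 2 × 3 = 36. If Days 1, 3 and 5 means one week per cycle, 6 × 3 = 18.
- 7.3, or 12.3 read literally: 1 FUS day, 1 opening scan, 1 site assessed for opening, Level A only.
- 7.6.3 with closure shown on Day 5: 36 − 1 = 35 FUS days (18 − 1 = 17). With closure shown at the second or third rescan: 34 or 33 (16 on the shorter schedule).
- 7.6.3, opening scans: up to 6, covering 1 + 1 + 2 + 2 + 3 + 3 = 12 sites.
- 12.3 read as a hold until closure: same as 7.6.3.

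The 7.6.3 figures are upper limits. They assume every later session is given, with no DLT, progression or withdrawal.

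**Step 4. The 75% criterion**

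A subject not closed on Day 3 has already had the Cycle 1 opening scan, so a closure failure does not erase that first result. The criterion is affected more directly by failed openings. Illustration (assumed, and below the three-subject trigger in 12.6): 6 subjects, 2 of whom fail the first opening scan, while 4 open on all six scans.

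- Per subject on the first scan, all treated: 4/6 = 66.7%, whichever rule applies.
- Per subject, removed subjects excluded: 4/4 = 100%.
- Per scan, removal after failure: 24/(24 + 2) = 24/26 = 92.3%.
- Per scan, subjects retained: from 24/36 = 66.7% (all later scans fail) to 34/36 = 94.4% (all later scans open).

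The result can fall on either side of 75%. With scans as the unit, the MRI rule alone can move it. With subjects as the unit, the choice of analysis set moves it.

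**The case against.** The strongest reply is that the sections describe one pathway, loosely worded. Section 7.6.3 hands over to 12.3 only after three scans without closure, and 12.3 ends participation at the same point. A subject who closes therefore stays on study, and the bar on FUS in 12.3 reads naturally as a hold during rescanning. *Anomaly* in 7.3 can likewise be read with 13.2, which has the same structure and concerns incidental findings; failed opening and closure have their own definitions and rules in 7.6 and 12.3. On those two readings no contradiction remains.

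Much of this stands. The hold reading is plausible and would align 12.3 with 7.6.3, but 12.3 does not say when the bar ends. The incidental-finding reading of 7.3 is also possible. However, the sentence directly follows the statement that the scans check opening and closure, the term is undefined, and 13.2 already covers incidental findings. A site cannot tell whether 7.3 repeats 13.2 or adds to it.

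Three stronger inferences are not supported:

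- *All three rules conflict for opening MRIs too.* The steps in 7.6.3 and the FUS bar in 12.3 apply to closure only.
- *7.6.3 states that FUS resumes.* This is implied by the scheduled Day 5 session and the later cycle, but not stated.
- *The MRI rules are the main cause of the denominator problem.* It comes mainly from the undefined case in 10.1 and the missing analysis set in 10.2. Reconciling the MRI rules would not cure it.

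**Conclusion.** The point holds in limited form. For non-closure, the wording supports three incompatible consequences; for non-opening, at most two. The 7.3 limb rests on reading *anomaly* by its position after the opening and closure scans.

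The contrast of 1 FUS day and 1 opening scan with up to 6 opening scans requires literal readings and, under 7.6.3, a subject who completes all cycles. If 12.3 is a hold until closure, the contrast is between 7.3 and the other two sections. If 7.3 also means incidental findings only, what remains is a lack of clarity: two undefined terms and an unstated end to the FUS hold. A reader might infer that 12.3 permanently bars FUS after one open scan; the text permits this but does not settle it.

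The effect on the 75% result is real but secondary. The documents do not determine which clinical rule should apply, and none is preferred here.

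**What to change.** Reconcile 7.3, 7.6.3, 12.3 and 13.2, preferably in one table to which all four refer. For each MRI result (not open, not closed, other or incidental abnormality), state one consequence for FUS, for drug and for study participation. Define *anomaly* and *irregular*, or replace them with the definitions in 7.6.1 and 7.6.2. State whether the FUS bar in 12.3 is permanent or ends when closure is shown, and whether 7.3 covers anything beyond 13.2. The sponsor decides the clinical consequence in each cell.

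In 10.1 and 10.2, state that subjects removed or held because of an MRI result stay in the denominators of the 75% opening criterion and the safety analysis. For this to work, 10.1 must also say whether a case is a subject, a scan or a site.

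The cost is a wording amendment; sample size and data collection need not change.

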7.5 Treatment MRIs

Treatment MRI breakdown:

- 1 cycle of Panobinostat= 2 weeks of 3 alternate treatment days. Subjects will undergo 6 cycles, each spaced 1 week apart.
- In each cycle, subjects will receive Focused Ultrasound (NgFUS) and injection of DEFINITY® microbubbles using NgFUS system in the Radiation Oncology Suite on Days 1, 3, and 5 (all treatment days).
- **MRI to Determine Opening of Blood Brain Barrier:** On Week 1 Day 1 of each cycle, 2-4 hours post FUS treatment with DEFINITY® microbubbles on Day 1, subjects will receive an MRI with injection of Gadolinium contrast.
- Treatment includes receiving Oral Panobinostat at 15 mg/m² on the days of NgFUS treatment.
- **MRI to Confirm Closure of Blood Brain Barrier:** On Week 1 Day 3 of every other cycle (Cycles 1, 3 and 5), subjects will undergo MRI with gadolinium pre Day 3 FUS treatment to ensure closure of the blood brain barrier. This MRI will be conducted within 24-48 hours of the completion of the Day 1 FUS treatment.
- A number of tumor sites (NOTS) escalation scheme for the number of tumor sites targeted by FUS will be followed as laid out in [section 7.2](#). As stated in the section, an MRI (without contrast) will be performed prior to each escalation to clear the subject of any possible DLTs and increase in tumor size.

Subjects will receive FUS treatment in the Radiation Oncology Suite and drug treatments in either the Outpatient Clinic on HIP-7 or in Radiation Oncology immediately after the FUS treatment. Subjects will be monitored by the study team with Neurological Exams on treatment days, as determined necessary. Subjects will not be kept as inpatients for treatment days and will be discharged following completion of treatment day, unless deemed necessary by the study team.

See [Appendix A](#) and [B](#) on pages 47 and 49 respectively for a detailed breakdown of visits and data collected.

7.6 Opening and Closing of the BBB

7.6.1 Radiological Evidence of the BBB Opening

The BBB will be determined to be open if within 5mm of site of FUS, there is evidence of enhancement seen on T1 weighted post contrast images.

7.6.2 Radiological Evidence of BBB Closure

The BBB will be determined to be closed if within 5mm of site of FUS, there is no evidence of enhancement seen on T1 weighted post contrast images.

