2.2 Preclinical studies using FUS with microbubbles

Focused ultrasound (FUS) has been extensively studied in safely opening the blood-brain barrier (BBB) of various animal species and different disease-mimicking models. The application of FUS in conjunction with preformed intravenously administered microbubbles (i.e., DEFINITY®) produces bio-effects, which are confined only within the targeted region. Multiple studies have demonstrated that this targeted drug delivery system can be successfully applied in preclinical studies on rodents, rabbits, and non-human primates (NHP). This technique has shown efficacy in safely delivering a wide range of drugs such as contrast agents, sugars, antibodies, viruses, chemotherapeutics and neurotrophic factors into the brain [13-31]. The safety of opening the blood brain barrier using focused ultrasound was further proved in a murine pre-clinical study conducted by Englander et. al. that aimed to determine the safety and feasibility of this technique in a murine pontine glioma model. In this study mice were randomly assigned to control, FUS and double-FUS groups. Pulse and respiratory rate were continuously monitored during treatment. BBB opening was confirmed with gadolinium-enhanced MRI and Evans blue. The study showed that FUS successfully caused BBB opening while preserving normal cardiorespiratory and motor function.

Furthermore, FUS-mediated BBB opening has been shown to effectively decrease the amyloid plaque load and restore memory in rodents with Alzheimer's disease (AD), even without the administration of a drug [22]. These rodents were tested behaviorally and showed significant memory improvement following FUS treatment.

DEFINITY® Microbubbles are gas-core, lipid-shelled particles with diameters between 1-10 μm [32]. Their minute size allows them to circulate throughout the vasculature. DEFINITY® Microbubbles are compressible; thus, they respond to the alternating phases of an ultrasound wave by expanding and contracting, a response known as acoustic cavitation. These volumetric oscillations exert stresses onto the surrounding vascular walls and temporarily open the tight junctions that formulate the BBB. The magnitude and distribution of this bio effect can be controlled by adjusting the sonication parameters but is typically constrained within the center of the focal volume (Figure 1).

[figure not shown]

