Figure 1: BBB opening within the targeted area of an NHP brain. The induced bioeffect is constrained within the center of the focal volume. Adapted from Karakatsani et al, 2017.

[name] group and others have published extensive work confirming the accuracy and safety of this technique performed both in rodents, in NHP and, more recently, is being investigated in humans. [name] research has recently shown that safe BBB opening can be achieved in an NHP model using clinically relevant acoustic pressures (i.e., mechanical index (MI) of 0.4) and the clinically recommended dose for imaging applications of DEFINITY® microbubbles, which are the parameters proposed for this clinical trial. Therefore, [name] et al has established that this technique is able to safely open the BBB and achieve targeted drug delivery in the brain using acoustic intensities far below the FDA limits for ultrasound imaging and drug doses equal to those routinely used in the clinic. In a study by [name], the integrity of the BBB was restored within hours, depending on the selected parameters, e.g. the acoustic pressure or pulse length [27]. Permeability and volume of opening were both found to increase with the acoustic pressure and pulse length, but closing occurred within 48 to 72 hours in these cases. BBB can be safely and reversibly opened using focused ultrasound and DEFINITY® microbubbles, and that its integrity is restored within 2 days in rodents and between 2 and 4 days in NHPs.

All of [name] nonclinical laboratory studies have been conducted in compliance with applicable requirements in the Good Laboratory Practice (GLP) regulations in 21 CFR Part 58 (See Appendix attached 5.0).

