The device will be operated at the same specifications as that in adults and other NHP studies since the FUS propagation will be simulated through the skull on a patient-by-patient basis based on the MRI, or CT obtained during radiation planning at the time of diagnosis (if available). CT scans will not be performed for the purposes of this research study. Extensive work has been done at [name] lab using human skull fragment and simulation, demonstrating that due to the low frequency of the FUS device (i.e., 0.25 MHz), significant skull-induced beam aberrations are not expected. In an adult skull, the focal shift is on the order of a few mm. Therefore, we expect a lower shift through the thinner skull of pediatric patients. The acoustic field will be simulated based on the CT of each patient, if available. Otherwise we will use the MRI scan to acquire structural information about the skull geometry. The 3D simulation will be performed using the kWave toolbox in Matlab. The simulation will be conducted first in free-field (i.e., only water) and then using the CT/MRI scan of the patient, to calculate the attenuation coefficient at a defined beam trajectory and transducer location. No assumptions regarding bone properties are required (if a CT scan is available), since the speed of sound is directly derived from the Hounsfield units of the CT scan. If a CT is not available, we will use the skull contour from the MRI and assume a bone density of 1.35 g/cm³ (this is the average skull density in pediatric patients [47]). We will perform a total of at least 10 simulations, by allowing a margin of +/- 2mm Euclidian error and +/- 20° angular error. The attenuation coefficient and derated pressure will be calculated as average values across all the simulations. The device will not need maintenance but will be calibrated once every 6 months using a hydrophone. Please see device specifications attached in appendix 7.0.

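### BBB opening and closure are scored on any enhancement near an undefined site, without reference to the pre-treatment scan, so pre-existing enhancement reads as open and can never read as closed.

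*Combined protocol and SAP*

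**What the plan says.** Section 7.6.1 defines opening: "The BBB will be determined to be open if within 5mm of site of FUS, there is evidence of enhancement seen on T1"-weighted post-contrast images. Section 7.6.2 defines closure as the absence of the same sign: "The BBB will be determined to be closed if within 5mm of site of FUS, there is no evidence of enhancement". Both are presence-or-absence rules applied to a single scan.

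Section 7.3 aims FUS at non-enhancing tissue around the tumour. It accepts that some enhancement may precede treatment and expects a clear increase afterwards. On the size of the focus it says: "The focal area is quite big (6mm x 6mm x 49mm), so there should be clear opening in the neighboring non-enhancing tissue". It also requires a contrast MRI no more than 7 days before the procedure.

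The definitions are used in several places:
- Section 10 refers to 7.6 for evidence of successful opening and closing.
- Section 10.1 sets success at safe opening in at least 75% of cases on MRI.
- Section 7.6.3 ties its steps after a failed closure scan to the definitions in 7.6.1 and 7.6.2.
- Section 12.3 takes a subject off study if closure is not shown after three MRIs.
- Section 12.6 requires contact with the FDA if the settings fail to open the barrier in 3 subjects.

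**The concern.** The rule in 7.6 does not measure what section 7.3 says should happen. Section 7.3 describes an increase over the pre-treatment state; 7.6 asks only whether enhancement is there. If a subject already has enhancement within the reading zone, the post-FUS scan is read as open whatever FUS did. The Day 3 scan is then read as not closed for as long as that enhancement persists.

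The two errors act on different results. A false open reading inflates the feasibility proportion and can hide a failure that section 12.6 is meant to count. A permanent not-closed reading sends the subject down the path in 7.6.3 and 12.3 for a reason unrelated to FUS, and then appears in the results as failure to close.

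The second gap is the term *site of FUS*, which is never defined. Against a focus 49 mm long, 5 mm from a point and 5 mm from the edge of the sonicated volume are very different regions. Two readers could score the same scan differently.

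**Working it through.** **The plan's own figure.** Section 10.1 gives 6 subjects for a change of 72 mm³ with SD 50 mm³, α = 0.05, power 0.80, paired t-test. Standardised effect = 72/50 = 1.44. Two-sided noncentral-t power is 0.677 at n = 5 and 0.803 at n = 6. The figure reproduces and is not in dispute. It is itself built on an after-minus-before difference.

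**Baseline: all combinations under the wording of 7.6.**

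| Enhancement within 5 mm before FUS | FUS effect | Post-FUS reading | Reading after the effect has resolved |
|---|---|---|---|
| No | Yes | Open (right) | Closed (right) |
| No | No | Not open (right) | Closed (right) |
| Yes, persisting | Yes | Open (right) | Not closed (wrong) |
| Yes, persisting | No | Open (wrong) | Not closed (wrong) |

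Scoring change from the pre-treatment scan corrects the three wrong cells, provided the baseline enhancement is stable.

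**Effect on the 75% criterion.** Assume one case is one subject; the plan does not define a case.
- At the maximum of 15: 0.75 × 15 = 11.25, so 12 openings are needed. 12/15 = 80% passes; 11/15 = 73.3% fails.
- At the 6 of section 10.1: 0.75 × 6 = 4.5, so 5 are needed. 5/6 = 83.3% passes; 4/6 = 66.7% fails.

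At either size, one subject read as open because of baseline enhancement is enough to change the conclusion when the count is at the boundary. The documents do not say how many subjects will have such enhancement, so the expected bias cannot be calculated.

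**Region.** Inputs: 5 mm (7.6) and a 6 × 6 × 49 mm focus (7.3).
- Point reading, length: 2 × 5 = 10 mm; 10/49 = 20%.
- Point reading, ellipsoid with semi-axes 3, 3 and 24.5 mm: volume = (4/3)π × 3 × 3 × 24.5 = 924 mm³. A centred sphere of radius 5 mm overlaps it by about 253 mm³; 253/924 = 27%.
- Point reading, box: 6 × 6 × 49 = 1,764 mm³; about 18% lies inside the sphere.
- Volume reading (whole focus plus 5 mm): 100%.

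**From acoustic focus to opened barrier.** These are shares of the focus, not of opened tissue. The planning change of 72 mm³ is 72/924 = 8% of the ellipsoid. If an opening of that size had the shape of the focus (an assumption), its length would be 49 × (72/924)^(1/3) = 21 mm, and about 65% of its volume would lie inside the centred 5 mm sphere. If it were a compact sphere, its diameter would be 2 × (3 × 72/4π)^(1/3) = 5.2 mm and, centred on target, it would lie wholly inside.

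**The case against.** **Intent is already change from baseline.** Section 7.3 expects a clear increase, section 10.1 compares each patient's scan with the one before opening, and section 10.2 tests before against after. Sections 7.3 and 10 also prefer non-enhancing targets, which should make the problem uncommon. All of this is fair and limits the likely size. But the open and closed calls rest on 7.6, which does not carry that intent, and section 10 calls the non-enhancing choice ideal, not required.

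**Site may mean the opened region.** Section 10 also uses the word for the part of the barrier that was opened, and section 7.2 equates the number of sites with the number of openings. This stands: the point reading is one of two, so the region issue is an ambiguity and not a demonstrated shortfall.

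**Tempting stronger reading.** A reader might infer that a barrier still open along most of the beam can be called closed, or that 73% of the opened barrier goes unread. The documents do not support this. Section 2.2 says the effect "is typically constrained within the center of the focal volume", and also that "Permeability and volume of opening were both found to increase with the acoustic pressure and pulse length", which gives no reason to expect the ends of the focus to outlast its centre. The 73% is a share of the acoustic focus. Displacement could cause a partial miss: "In an adult skull, the focal shift is on the order of a few mm", with less expected in children. That is far from most of the beam.

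**Closure scans release few sessions.** They are scheduled only on Week 1 Day 3 of cycles 1, 3 and 5, so three checks against up to 6 × 2 × 3 = 36 sessions. This also stands. The closure call matters at those points and at repeat scans, not before every sonication.

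**Other clauses may catch stray enhancement.** Sections 7.3 and 12.3 act on MRI anomalies or irregular scans. Neither term is defined, so neither settles how a scan is scored.

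**Conclusion.** The concern holds on baseline. As worded, 7.6.1 and 7.6.2 misclassify any subject with persisting enhancement within the zone: always open, never closed. This follows from the text and needs no assumption beyond section 7.3's own allowance for such enhancement. Its frequency is unknown. With one case per subject, a single such reading can decide the 75% criterion at n = 6 or n = 15.

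The region point holds only as an undefined term. Depending on the reading, coverage runs from about 20% of the focal length (18% to 27% of focal volume) to all of it. A false closed call is possible under the point reading but is not the pattern the protocol leads one to expect. For opening, a narrow zone would miss displaced openings and so lower the success proportion, the opposite direction to the baseline error.

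**What to change.** For the imaging outcome:
1. In 7.6.1 and 7.6.2, score opening and closure as change from the pre-treatment contrast MRI, which section 7.3 and Appendix A already require.
2. Define the site, and state the region read relative to the sonicated volume and how enhancement elsewhere in that volume is recorded.
3. Reconcile 7.3, 7.6.1, 7.6.2, 10.1 and 12.3 so that they use the same definition.
4. Name the comparator scan for later cycles. The pre-cycle checkpoint MRIs in section 7.2 are without contrast, so the screening scan may be the only contrast baseline, and tumour progression since then could be mistaken for opening or for failure to close.

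No extra scan is needed for the basic comparison. The cost is slightly more reading work, and some scans may change category. A wider region would make open easier to declare and closed harder, so the choice should be made before scans are read. Because 7.6.3 and 12.3 act on these calls, the sponsor must also say how the imaging definition relates to them; no rule for giving or withholding treatment is proposed here.
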